## **9.4 Primary Efficacy Analysis**

The primary efficacy analysis will be performed on the FAS population.

For the primary efficacy endpoint, change from baseline in AISRS at Visit 7 (Week 5), the two AR19 dose levels (20 and 40 mg/day) will be compared with placebo. To account for these comparisons, a Bonferroni multiple comparison adjustment will be utilized. Both comparisons will be conducted at the 0.025 (0.05/2) alpha level. No other adjustments for multiplicity will be applied to any other endpoints or comparisons.

Change from Baseline in AISRS at Visit 7 will be compared between each of the two different AR19 dose groups and the placebo group using a restricted maximum likelihood (REML)-based mixed model for repeated measures (MMRM). This model will include fixed effects for treatment, week, baseline AISRS, and the treatment-by-week interaction. Study week will be included in the model as a categorical variable. Within this model, pairwise comparisons (using least squares [LS] mean contrasts) will be made to compare AISRS at Visit 7 for each AR19 dose level with placebo separately (primary efficacy outcome). Treatments will also be compared at other weeks as secondary analyses. If differences between baseline characteristics exist between the three treatment groups in this comparison, it will be investigated whether adjustment for these characteristics is clinically relevant and necessary as a sensitivity analysis.

All available data will be used; there will be no imputation of missing data.

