7.4 Analysis Methods

7.4.1 Primary Efficacy Analyses – AISRS Total Scores

The primary efficacy analysis will be performed on the FAS population. The primary efficacy outcome is the change from baseline in AISRS total score at Visit 7 (Week 5) in AR19 (20 and 40 mg/day) versus placebo. To account for these comparisons, a Bonferroni multiple comparison adjustment will be utilized. Both comparisons will be conducted at the 0.025 (0.05/2) alpha level. No other adjustments for multiplicity will be applied to any other endpoints or comparisons. Change from Baseline in AISRS at Visit 7 will be compared between each of the two different AR19 dose groups and the placebo group.

The key elements of the primary efficacy analysis are as follows:

Data: AISRS total scores measured at Baseline through Visit 7. All available data will be used; there will be no imputation of missing data.

Model: Restricted maximum likelihood (REML)-based MMRM analysis

Fixed effects: The following fixed effects are planned:

- Treatment (class effect: AR19 20 mg/day, AR19 40 mg/day, placebo)
- Week (class effect: Weeks 1, 2, 3, 4, 5)
- Baseline AISRS total score
- Treatment-by-week interaction

Residual Variance-Covariance Matrix: An unstructured correlation matrix will be used to model the within-patient errors and restricted maximum likelihood estimation will be used. The Kenward-Roger method will be used for the denominator degrees of freedom. Should the model fail to converge with an unstructured covariance matrix, alternative covariance structures will be applied, in the following order, until the model converges: heterogeneous Toeplitz, heterogeneous compound symmetry, then heterogeneous autoregressive(1).

The null hypothesis:

H_0 : Change from baseline AISRS total scores at Visit 7 are the same for AR19 and placebo

will be tested against the two-sided alternative hypothesis

H_1 : Change from baseline AISRS totals scores at Visit 7 are not the same for AR19 and placebo.

Within this model, pairwise comparisons (using least squares [LS] mean contrasts) will be made to compare AISRS at Visit 7 for each AR19 dose level with placebo separately (primary efficacy outcome). Treatments will also be compared at other weeks as secondary analyses. If differences between baseline characteristics exist between the three treatment groups in this comparison, it will be investigated whether adjustment for these characteristics is clinically relevant and necessary as a sensitivity analysis.

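### The primary MMRM fits one baseline AISRS slope for all five weeks; a baseline-by-week term would cost four parameters and could modestly sharpen the Visit 7 contrast

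*SAP*

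**What the plan says.** SAP 7.4.1 lists four fixed effects: a three-level treatment factor, "Week (class effect: Weeks 1, 2, 3, 4, 5"), "Baseline AISRS total score", and "Treatment-by-week interaction". Protocol 9.4 agrees: "This model will include fixed effects for treatment, week, baseline AISRS, and the treatment-by-week interaction". The efficacy text in the protocol synopsis is the same. No section contains a baseline-by-week term.

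The rest of the model is flexible over time. In SAP 7.4.1, "An unstructured correlation matrix will be used to model the within-patient errors", with Kenward-Roger degrees of freedom. The fallback structures are heterogeneous Toeplitz, compound symmetry and first-order autoregressive.

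The test concerns the last visit only: LS mean contrasts are used "to compare AISRS at Visit 7 for each AR19 dose level with placebo separately (primary efficacy outcome"). On multiplicity, "Both comparisons will be conducted at the 0.025 (0.05/2) alpha level", and the null "will be tested against the two-sided alternative hypothesis".

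**The concern.** The model lets the treatment effect and the residual covariance differ freely by week, but it requires the regression of change on baseline to be identical at Weeks 1 to 5. That regression slope equals cov(score at week, baseline) / var(baseline), minus 1. A constant slope therefore means that baseline covaries equally with every later visit. The plan does not impose this on any pair of post-baseline visits, and two of its fallback structures expressly let correlation change with lag.

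If correlation with baseline weakens with time, the slope at Week 5 differs from the slope at Week 1 in every arm. Visit 7 is then adjusted with the wrong slope for that visit, and part of the variance that baseline could explain is left in the residual. What is at stake is precision of the primary contrast.

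**Working it through.** **1. The plan's own sample size.** From SAP 2.7: difference 7.0, SD 13.0, two-sided alpha 0.025, about 90% power. Normal approximation: 2 × (2.2414 + 1.2816)² × 13² / 7² = 85.6, so 86 per group. By the noncentral t, power is 89.7% at 86 and 90.0% at 87. The stated 87 reproduces.

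**2. Parameters.** Three arms by five weeks give 15 means. Adding one baseline slope makes 16; adding five makes 20. The cost is four.

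**3. Large-sample formula (complete data).** Let *b* be the five weekly slopes, *S* the residual covariance given baseline, and SD_b the baseline SD.
- The common-slope model estimates b* = 1′S⁻¹b / 1′S⁻¹1, a weighted average over all five visits, Visit 7 included.
- Visit 7 variance per subject, common slope: S₅₅ + (b₅ − b*)² × SD_b².
- With baseline-by-week: S₅₅.

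The gain depends on b₅ − b*. Drift that leaves the two equal gives none.

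**4. Assumptions.** The documents give no baseline SD, slopes or within-subject correlation. Entry requires a score of at least 26 on a scale ending at 54; I took SD_b as 5, 7 or 9. The total SD of change was held at 13.0, so S₅₅ = 169 − (b₅ × SD_b)². Slopes run linearly from Week 1 to Week 5. Three residual patterns were used: (A) correlation 0.6, equal SDs; (B) correlation 0.7, SD rising from 70% to 100% of the Week 5 value; (C) autoregressive 0.8, SD rising as in B.

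**5. Worked case: SD_b = 7, slopes −0.2 to −0.5.** S₅₅ = 169 − 12.25 = 156.75, SD 12.52.
- A: b* = −0.35; added variance 0.15² × 49 = 1.10; SD 12.56; SE falls 0.35%.
- B: b* = −0.195; added 0.305² × 49 = 4.56; SD 12.70; SE falls 1.42%.
- C: b* = −0.27; added 0.23² × 49 = 2.59; SD 12.62; SE falls 0.82%.

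At 87 per group, power rises to 92.2% from 92.0%, 91.4% and 91.8% respectively.

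**6. Range over all SDs and patterns.**

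| Slope, Week 1 to Week 5 | Fall in Visit 7 SE | Power gain (points) |
|---|---|---|
| −0.4 constant | 0% | 0 |
| −0.3 to −0.5 | 0.1–1.1% | 0.1–0.5 |
| −0.2 to −0.5 (moderate) | 0.2–2.4% | 0.1–1.2 |
| −0.1 to −0.6 (strong) | 0.5–6.7% | 0.2–3.4 |
| 0 to −0.8 (extreme) | 1.3–17% | 0.6–8 |

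**7. Simulation with dropout.** 150 trials per pattern, 104 per arm, about 20% dropout depending on the last observed change, SD_b = 7, pattern B. With the extra term the SE rose about 0.1% for a constant slope (1.862 to 1.865). It fell 1.3% for moderate drift (1.857 to 1.832), 3.7% for strong drift (1.873 to 1.804) and 9.9% for extreme drift (1.910 to 1.720). Mean estimates under the two models were −7.02 and −7.02, −7.02 and −7.06, −6.67 and −6.75, −6.90 and −6.89: never more than 0.08 apart.

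**8. Drift in one arm only.** Take slopes −0.1 to −0.5 with SD_b = 7. If all arms drift, pattern A adds 0.2² × 49 = 1.96 to 156.75 (SE falls 0.6%). Pattern B has b* = −0.093 and adds 0.407² × 49 = 8.1 (SE falls 2.5%). If only one of three equal arms drifts, the arm-average drift is one third, so the variance removed is one ninth: 0.22 and 0.90. The SE then falls only about 0.1% and 0.3%.

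**The case against.** The planned model is legitimate, prespecified and identical in three places. A single baseline covariate with unstructured covariance is a recognised MMRM, and randomization keeps its contrast unbiased on average with complete data. All of that stands. Four stronger readings are tempting, and the documents do not support them.

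- **Titration makes the slope drift.** Under the titration tables (Protocol 5.3), only the 40 mg arm steps up over three visits. The 20 mg arm has one increase and placebo none. Drift caused by dose would be arm-specific, and a slope shared by all arms captures little of it (step 8). The case rests instead on correlation with baseline changing over time, which can occur in every arm and needs no dose effect.
- **The Visit 7 adjustment uses only earlier visits.** It does not: the pooled slope includes Visit 7.
- **The common slope biases the result under dropout.** No bias was shown. The two models' mean estimates differed by less than 0.1 point, against a design difference of 7.0. Chance baseline imbalance is adjusted with a slightly wrong slope, but this averages out over randomizations and is part of the variance counted above.
- **The gain is large.** A fall in SE near 10% appears only under strong-to-extreme assumed drift. Nothing in the documents indicates the actual slopes.

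It can also be said that the edit reaches beyond one SAP line. That is correct, and the fix allows for it.

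**Conclusion.** The point holds as an optional efficiency refinement. One baseline coefficient is used for five weeks, and the Visit 7 contrast loses some precision whenever the Week 5 slope differs from the covariance-weighted pooled slope. The payoff is asymmetric: about 0.1% in SE at worst if the slope is constant, against falls of about 0.2 to 2.4% under moderate drift and 0.5 to 7% under strong drift. In power, moderate drift is worth about one point or less.

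These ranges rest on assumed slopes, baseline SD and covariance, and on a total SD of 13.0. The treatment difference being estimated does not change. The planned analysis would remain valid without the term.

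**What to change.** Before unblinding:

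- Add a baseline AISRS total score-by-week interaction to the fixed effects in SAP 7.4.1, and the matching baseline subscale-by-week term to the AISRS subscale models in SAP 7.4.2.
- Carry it into the analyses that refit this model: placebo-based imputation and tipping point (SAP 7.1.1.2) and the per-protocol repeat (SAP 7.3.2).
- Record the change in SAP 12.2, which now states that no analysis changes from the protocol are planned, and align Protocol 9.4 and the synopsis.

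BRIEF-A, DERS and ASQ need no such term, since Visit 7 is their only scheduled post-baseline assessment apart from early termination.

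The timing matters because SAP 10 treats analyses added after SAP finalization as exploratory. The cost is four extra parameters among about 312 subjects and minor document edits. The parameters matter only in small subgroup fits (SAP 7.6), such as a sparse ADHD-type stratum; the SAP could state there that the interaction is dropped if the subgroup model does not converge.

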## **1.3 Rationale for Dose Selection**

AR19 will be available in 10 mg and 20 mg strengths for this study.

Although there is limited information regarding dosing of amphetamine-based IR products in adults, the Food and Drug Administration (FDA) has approved several extended-release amphetamine-based products for the treatment of ADHD in adults.

In the Evekeo® children classroom study, the median optimized daily dose was 20 mg. In general, adults have lower systemic exposure to amphetamines when receiving the same fixed dosage and formulation.

For one longer-acting amphetamine mixed salt formulation, the maximum dosage was 50 mg (31.3 mg amphetamine equivalents). The maximum daily dose of 40 mg that will be used in this study has 29.3 amphetamine equivalents. AR19 is a 50-50 mixture of d- and l-amphetamine, it is anticipated that the side effect profile of the 40 mg dose should not be substantially greater. Therefore, the 20 and 40 mg daily doses used in this study are expected to show efficacy and establish the safety profile of AR19 in adults.

AR19 will be given twice daily: the first dose on awakening and the second dose four to six hours later. The double-dummy technique will be utilized in order to maintain the blind between the 10 mg and 20 mg capsules and matching placebo.

In adults, the starting dose will be 10 mg once daily the first week and 10 mg twice per day the second week. In subsequent weeks, subjects randomized to 10 mg twice per day (20 mg daily) will remain on that dose until the final visit, while subjects randomized to 20 mg twice per day will be raised in increments of 10 mg/week with completion of titration at Visit 5 (Week 4) and remain on their randomized dose (40 mg/day) for the final visit. Subjects who experience unacceptable tolerability will be discontinued.

The efficacy and safety profile of amphetamine is well established, and recent studies continue to support the safe and effective use of amphetamine for the treatment of ADHD.

The use of amphetamine in the treatment of ADHD is endorsed by professional medical organizations including the National Institute for Health and Care Excellence and the European Network Adult ADHD.

There are no published professional guidelines for the treatment of adult ADHD by professional organizations in the United States.

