2.6 Treatment Regimens

The following dosing procedures will be followed:

- The dosing regimen will be two capsules twice daily. All subjects will be instructed to take their first dose (two different colored capsules) of study medication in the morning. The second dose (two different colored capsules) should be taken four to six hours later.
- Study medication will be administered orally by swallowing the capsules.
- Study drug can be taken with or without food.

This study is a fixed dose regimen. Dose adjustments are not allowed during the study.

After Screening and Baseline evaluations are complete, eligible subjects will be randomized 1:1:1 to one of two fixed-dose groups (AR19 10 mg p.o. b.i.d. or AR19 20 mg p.o. b.i.d.) or placebo.

Subjects unable to tolerate their AR19 dose at any time during study drug administration will be withdrawn from the trial.

Subjects will begin dosing with double-blind study drug the morning following the Baseline visit. The first dose will be taken in the morning (2 capsules) and the second dose (2 capsules) will be taken 4 to 6 hours later.

Table 2.6.1 Titration Scheme for 20 mg Daily Dose

Kit Assigned on Visit/Day	First Dose		Second Dose	
Visit 2, Day 1	20 mg Placebo	10 mg	20 mg Placebo	10 mg Placebo
Visit 3, Day 8	20 mg Placebo	10 mg	20 mg Placebo	10 mg
Visit 4, Day 15	20 mg Placebo	10 mg	20 mg Placebo	10 mg
Visit 5, Day 22	20 mg Placebo	10 mg	20 mg Placebo	10 mg
Visit 6, Day 29	20 mg Placebo	10 mg	20 mg Placebo	10 mg

Table 2.6.2 Titration Scheme for 40 mg Daily Dose

Kit Assigned on Visit/Day	First Dose		Second Dose	
Visit 2, Day 1	20 mg Placebo	10 mg	20 mg Placebo	10 mg Placebo
Visit 3, Day 8	20 mg Placebo	10 mg	20 mg Placebo	10 mg
Visit 4, Day 15	20 mg	10 mg Placebo	20 mg Placebo	10 mg
Visit 5, Day 22	20 mg	10 mg Placebo	20 mg	10 mg Placebo
Visit 6, Day 29	20 mg	10 mg Placebo	20 mg	10 mg Placebo

Subjects randomized to placebo will receive the 10 mg and 20 mg placebo capsules for the first and second dose (4 capsules/day) during the trial.

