8.3 Extent of Exposure

The length of exposure (in days) of study medication will be calculated based on the dates of first and last dosing of study medication (last dosing date - first dosing date + 1), by treatment and overall. Length of exposure will be summarized by treatment group on the Safety population as continuous values and for the following categories (which correspond to scheduled study visit timing): 1-7 days, 8-14 days, 15-21 days, 22-28 days, and >=29 days.

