8.4 Adverse Events

All AEs will be coded using MedDRA Version 21.0.

An AE is considered treatment-emergent, if it started on or after the first dose of study medication is administered. If a subject terminates early from the study and has an AE after his/her last dosing date, the AE will be deemed as treatment-emergent if it occurs \leq 24 hours after the last dose and not as treatment-emergent if it occurs $>$ 24 hours after the last dose of study medication. AEs with partial start dates will be imputed as outlined in Section 8.1.

Summary Tabulations

An overview of the frequency, i.e., the number and percentage of subjects with at least one of the following AEs will be presented by treatment group:

- Treatment-emergent adverse events (TEAEs).

- TEAEs related to study medication.
- Severe TEAEs.
- Serious treatment emergent AEs (SAEs).
- SAEs related to study medication.
- AEs leading to death.
- AEs leading to premature withdrawal of study medication.

System Organ Class/Preferred Term Tabulations

The frequency of subjects reporting TEAEs will be summarized within each system organ class (SOC), preferred term (PT), and treatment group. The SOC terms and PTs will be presented in decreasing order of the total number of subjects (frequency) who experienced each adverse event. System organ class terms and PTs with the same frequency will be presented alphabetically.

If a single subject experiences the same AE more than once, the subject will be counted once per SOC and PT for that AE, using the most severe intensity or highest relationship to study medication.

The frequency of subjects reporting the following TEAEs will be presented:

- All TEAEs.
- All TEAEs by intensity.
- All TEAEs by relationship to study drug.
- All treatment-emergent SAEs.
- All TEAEs leading to premature discontinuation from study.

By-Subject Listings

By-subject listings including relevant information (i.e. treatment, age, sex, race, duration of AE, severity, relationship, outcome, action taken, etc.) will be presented for:

- All AEs.

- SAEs.
- AEs leading to death.
- AEs leading to premature discontinuation of study medication.

The onset of AEs will be calculated relative to the first dose of study medication. The duration of AEs in days will be calculated as the difference between the onset and resolution dates of the AE. If the AE is ongoing at the end of the study, or the resolution date is unknown, the duration will be presented as 'Unknown'.

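### The two AR19 arms take the same scheduled dose through Week 2, but the by-week contrasts stay split by target dose and the safety tables have no breakdown by daily dose

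*SAP*

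**What the plan says.** **Dosing.** Protocol 1.3 gives one start for all AR19 subjects: "the starting dose will be 10 mg once daily the first week and 10 mg twice per day the second week". The kit tables in Protocol 5.3 and SAP 2.6 ("Table 2.6.1 Titration Scheme for 20 mg Daily Dose" and "Table 2.6.2 Titration Scheme for 40 mg Daily Dose") agree. They have identical rows for the Visit 2 and Visit 3 kits and differ from the Visit 4 kit onward.

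**Efficacy.** The mixed model in SAP 7.4.1 has a three-level treatment factor (20 mg/day, 40 mg/day, placebo) crossed with Weeks 1 to 5. The primary contrasts are at Visit 7. The section then says: "Treatments will also be compared at other weeks as secondary analyses". SAP 7.4.2 also compares treatments at each time point for CGI-S and CGI-I. No contrast combines the AR19 arms at any week.

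**Safety.** SAP 8.3 says: "Length of exposure will be summarized by treatment group on the Safety population as continuous values", together with weekly duration categories. SAP 8.4 says: "The frequency of subjects reporting TEAEs will be summarized within each system organ class (SOC), preferred term (PT), and treatment group". Neither section plans days at each daily dose or events by dose at onset. The Safety Population is presented as treated and the FAS as randomised (SAP 4.1.1 and 4.1.2).

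**The concern.** At Weeks 1 and 2 the plan tests one blinded regimen against placebo twice, under two dose labels, with half of the AR19 subjects in each test. No true dose difference can exist at those weeks. If one arm crosses the significance level and the other does not, a reader of the weekly table could take chance for an effect of dose or a difference in onset. Each test is also less precise than the data allow. At Week 3 the column headed 40 mg/day holds ratings made on 30 mg/day.

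For safety, Protocol 1.3 expects the 20 and 40 mg doses to establish the safety profile of AR19 in adults. Dose adjustment is not allowed, and subjects who cannot tolerate study drug are withdrawn (Protocol 5.6). Some high-arm events and withdrawals may therefore occur before the subject ever takes 40 mg/day. The planned tables show them only under the arm's target dose.

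**Working it through.** **1. Scheduled dose behind each rating** (Protocol Tables 5.3.1 and 5.3.2; SAP Tables 2.6.1 and 2.6.2). I assume that each kit starts the morning after it is dispensed, as the protocol states for the first kit (Day 2), so each rating reflects the kit from the previous visit. Week numbers follow the schedule of events.

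| Rating | 20 mg arm | 40 mg arm |
|---|---|---|
| Week 1 (Visit 3) | 10 mg/day | 10 mg/day |
| Week 2 (Visit 4) | 20 | 20 |
| Week 3 (Visit 5) | 20 | 30 |
| Week 4 (Visit 6) | 20 | 40 |
| Week 5 (Visit 7) | 20 | 40 |

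Of the five weekly contrasts labelled 40 mg/day, two are at 40 mg/day. Of the five labelled 20 mg/day, four are at 20 mg/day.

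Two descriptions need reconciling with these tables. Protocol 1.3 ties Visit 5 to Week 4, whereas the schedule calls it Week 3 (the protocol may mean the start of the fourth treatment week). Protocol 3.1 and SAP 2.3 give four weeks of titration plus at least two stable weeks, which does not fit 35 dosing days.

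**2. Scheduled days at each dose, 40 mg arm** (Days 2 to 36): 7 at 10, 7 at 20, 7 at 30 and 14 at 40 mg/day.
- Below 40 mg/day: (7 + 7 + 7)/35 = 21/35 = 60%.
- Same as the 20 mg arm: 14/35 = 40%.
- Time-average dose: (70 + 140 + 210 + 560)/35 = 28 mg/day. In the 20 mg arm it is (70 + 20 × 28)/35 = 18 mg/day.

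**3. The plan's own sample size.** With difference 7.0, SD 13.0 and two-sided 0.025, a two-sample t test has power 0.900 at 87 per group. The stated figure reproduces, so these inputs are a fair base.

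**4. Precision at Weeks 1 and 2.** Assumption: the planning SD of 13, set for change to Visit 7, also holds at these weeks.
- Separate arms: SE = SD × √(1/n + 1/n). Pooled AR19: SE = SD × √(1/n + 1/(2n)).
- n = 87: 13 × √(2/87) = 1.97; 13 × √(1.5/87) = 1.71.
- n = 104 (randomised per arm, hence an upper bound): 1.80; 1.56.
- Ratio: √(1.5/2) = 0.866, a 13% reduction. With equal arm sizes and a common SD it depends on neither SD nor n. It equals the gain from one-third more subjects in every arm (1/0.75 = 1.33).

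**5. Power for an assumed early effect**, normal approximation, two-sided 0.025 (the default in SAP 3), n = 87, SD 13. Power = Φ(d/SE − 2.241).

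| Assumed effect d | Separate | Pooled |
|---|---|---|
| 3 points | 3/1.971 − 2.241 = −0.72 → 24% | 3/1.707 − 2.241 = −0.48 → 31% |
| 5 points | 5/1.971 − 2.241 = 0.30 → 62% | 5/1.707 − 2.241 = 0.69 → 75% |

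At 104 per arm, by noncentral t, a 5-point effect goes from 70% to 83%. At two-sided 0.05, the default in Protocol 9.2, the ranges at 87 per arm are 33–72% separate and 42–83% pooled.

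**6. Chance that exactly one of the two identical arms is nominally significant.** The two contrasts share the placebo arm, so their correlation is 0.5, and P = 2 × (p − P(both)), where p is the power of one contrast.
- SD 13, n = 87, 3 to 5 points: 25–32% at 0.025; 28–33% at 0.05.
- Assumed SD 9, 5 points, at 0.05: about 7% (n = 87) or 3% (n = 104).

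The documents give no early-week SD or effect, so this figure shows only that discordance can be common under some plausible settings.

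**The case against.** The strongest reply is that each AR19 arm is a forced-titration regimen, openly tabulated in the SAP. Comparing randomised regimens with placebo week by week is a legitimate, unbiased analysis, and a withdrawal during titration is an outcome of the assigned regimen. Onset is not an objective, the listed secondary outcomes are at Visit 7, and the other-week contrasts are supportive and unadjusted. AE onset is calculated relative to first dose and dosing is fixed, so scheduled dose at onset can be derived. Potentially clinically significant vital signs are shown by visit. Exposure-response goes to a separate pharmacokinetic SAP.

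Most of this stands, and it rules out several stronger readings that a reader might infer:
- *That the by-week comparisons are wrong or biased.* They are neither.
- *That the SAP presents Week 1 to 3 data as evidence on 40 mg/day.* It does not; it labels by regimen and leaves the inference to the reader.
- *That safety is tabulated by randomised arm.* Safety results are presented as treated. The gap is that the group label is not the daily dose at the time of the event.
- *That 21 days are counted as 40 mg exposure.* SAP 8.3 reports days on study medication and makes no claim about dose.

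The reply leaves two things open. The SAP already chooses to compare treatments at Weeks 1 and 2, and for identical regimens the pooled contrast is the more precise way to do so. And although scheduled dose at onset can be derived from listings, no planned adverse event table shows it.

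**Conclusion.** The point holds as a low-cost improvement to secondary and descriptive outputs. At Weeks 1 and 2 the planned contrasts have standard errors about 15% larger than a pooled contrast would (1/0.866 = 1.155) and invite a dose reading that the design cannot support. The adverse event and exposure tables do not separate titration from target-dose experience, although 60% of scheduled high-arm dosing days are below 40 mg/day.

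The 13% reduction in standard error needs only equal arm sizes and a common SD. The power gain (24–62% to 31–75%) further assumes SD 13 and 87 per arm at the early weeks, and effects of 3 to 5 points. The discordance probability is too sensitive to SD and effect to be given as one figure. The day counts are scheduled, not observed. Pooling has no place from Week 3 on, because the doses differ.

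The Visit 7 primary contrasts are at the full assigned doses. Neither their validity nor their alpha nor the sample size is in question.

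**What to change.** **SAP 7.4.1.** At Weeks 1 and 2, add the contrast ½(LS mean AR19 20 + LS mean AR19 40) − LS mean placebo from the same model, as the main AR19 comparison for those weeks. Keep the by-arm estimates there as descriptive. Annotate Weeks 1 to 3 in tables and figures with the scheduled daily dose in each arm. Leave Weeks 3 to 5 by arm and the primary contrasts as they are.

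**SAP 8.3 and 8.4.** Keep the by-group tables. Add (a) days at each daily dose and (b) a descriptive table of TEAEs, and of TEAEs leading to discontinuation, by scheduled daily dose at onset, with placebo for the same study weeks alongside.

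**SAP 12.2.** Record these as additions to the protocol analyses. Specify them before the SAP is final and the database is unblinded, because SAP 10 classes anything later as exploratory.

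**Cost.** One extra estimate at each of two weeks and two tables from dates already collected; no change to dosing, data collection or alpha. The drawback is that dose at onset is confounded with time on drug, so the new safety table is descriptive only and needs the same-week placebo column to be readable.
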